Acute lower respiratory tract infections (LRTIs) account for more than 27% of all hospitalizations among US children under five years of age, with recurrent LRTIs in children a recognized risk factor for asthma. Within rural areas of Montana, Alaska, and the Navajo Reservation, research has shown that residential biomass combustion leads to elevated indoor levels of fine particulate matter (PM2.5) that often exceed current healthbased air quality standards. Parallel findings have been observed in several developing countries where biomass combustion is commonly used for cooking and/or heating. This is concerning, as PM2.5 exposure is associated with many adverse health outcomes, including a greater than three-fold increased risk of LRTIs. Currently, there is a global effort to reduce indoor biomass smoke exposures in developing countries through the introduction of improved cookstove technology. Similar evidence-based efforts are warranted in rural and Native American communities in the US that suffer from elevated rates of childhood LRTI and commonly use wood for residential heating. To date, exposure reduction strategies in wood stove homes have been either inconsistently effective or include factors that limit widespread dissemination and continued compliance in rural and economically disadvantaged populations. In this project, we propose to test the efficacy of two intervention strategies for reducing indoor wood smoke PM2.5 exposures and children's risk of LRTI in three unique and underserved settings: (1) rural mountain valley communities in western Montana; (2) Navajo Nation communities; and (3) Alaska Native Villages. We will conduct a three-arm randomized placebo-controlled postonly intervention trial in wood stove homes with children less than five years old. Education on best-burn practices and training on the use of simple instruments (i.e., stove thermometers and wood moisture meters) will be introduced as one intervention arm (Tx1). This intervention will be evaluated against an indoor air filtration unit arm (Tx2), as well as a placebo arm (Tx3, sham air filters). The primary outcome will be LRTI incidence among children under five years of age. To allow for detection of exposure and outcome differences within each of the three regions, a sample of 324 homes, or 108 within each study area will be equally assigned to each of the three intervention arms. The overall hypothesis is that a low-cost, educational intervention targeting indoor wood smoke PM2.5 exposures will be sustainable, and can reduce children's risk of LRTI in underserved Native and rural communities.

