
This checklist submitted to the University of Montana IRB is specific for the activities in study area 1: rural mountain valley communities in western Montana. As indicated below (item #5) the other two study sites will fall under the jurisdiction of the respective local IRBs.

4.1 What do you plan to do with the results? If not discussed above, include considerations such as whether this is a class project, a project to improve a program/school system, and/or if the results will be generalized to a larger population, contribute to the general field of knowledge, and/or be published/presented in any capacity.

Results will be generalized to other communities and households that burn biomass for residential heating. Results of this research will be published in peer reviewer journals.

Is this part of a thesis or dissertation? No Yes If yes and other than the PI's, then whose?

5. IRB Oversight

Is oversight required by other IRB(s) [e.g., tribal, hospital, other university] for this project? Yes No
If yes, please identify IRB(s):

This study will be approved by The University of Montana Institutional Review Board (UM-IRB). Approval for study site 2 will be submitted to the Navajo Nation Human Research Review Board. Approval for study site 3 will be submitted to the Alaska Area Institutional Review Board (AAIRB), and the Yukon Kuskokwim Health Corporation Human Studies Committee.

6. Subject Information:

6.1 Human Subjects (*identify, include age/gender*):

Eligible subjects will include children less than 5 years of age that live in a household that utilizes a wood stove as the primary heating source in the study region (i.e., rural Montana). We anticipate an equal number of male and female child participants. A total of 108 households from this study area will be recruited for this study. We assume approximately 1.5 children under 5 years old per household (n = 162 total child subject).

6.2 How many subjects will be included in the study? 162

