- To not burn items other than wood (e.g., trash, cardboard, etc.)? _____
- To clean your flue and chimney? _____
- To condition or dry wood inside for 2 days before burning? _____
- To determine wood stove model and locate manual? _____

Statistical Analysis Plan

Analysis was conducted using R version 3.6.2 (The R Foundation for Statistical Computing, Austria). We calculated descriptive statistics for continuous variables (n, mean, standard deviation [sd], minimum [min], median, maximum [max]) and categorical variables (n, percentage of total) across all study households and separately for each treatment arm and study area. We averaged indoor concentrations of PM_{2.5} over the 6-day sampling period for each home and for the times during which each child was reported as being at the household.

Primary analyses were conducted within three model frameworks using the lme4 package (Bates et al. 2015): 1) intent-to-treat (ITT) framework with LRTI outcome (ITT-LRTI), 2) ITT framework with PM_{2.5} outcome (ITT-PM_{2.5}), and 3) exposure-response (ER) framework with LRTI as the outcome and PM_{2.5} as the exposure of interest. Although LRTI cases were collected as count data, very few children had more than one LRTI, resulting in under-dispersed data that violated the assumptions of attempted Poisson and negative binomial regression models. Thus, the ITT-LRTI framework utilized mixed effects logistic regression models (using the glmer function) with presence of LRTI (yes or no) as the outcome and assigned treatment as the exposure of interest. The ITT-LRTI models included a covariate for person-time at risk to account for the wide variability of child-weeks at risk across study participants. The models also included a covariate for child age (<1 year vs. 1 to 4 years) since randomization occurred within strata of this term. A nested random term (i.e., household:cohort:area) was included in the model to account for repeated measures clustered within household, cohort, and study area. The ITT-PM_{2.5} framework used mixed effects linear models (using the lmer function) with mean 6-day indoor PM_{2.5} concentration as the outcome and assigned treatment as the exposure of interest. Models were adjusted for child age and included a nested random term of cohort:area (there were no repeated measures within household for PM_{2.5}). Both ITT models utilized the study's randomization and were not adjusted for potential confounding variables in the primary analyses.

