We also conducted some post hoc sensitivity analyses for the ITT-LRTI framework with other model variations to provide insight into our primary model selection and results. Specifically, we assessed models that 1) used

study area (AK, NN, WMT) as a fixed effect rather than a random nested term, 2) removed the covariate for person-time at risk, and 3) removed the random nested term for household.

We evaluated potential modification of the effect of the treatments by a priori selected child, caregiver, and home characteristics within each of the model frameworks by including interaction terms in the primary model. We assessed significance of the interaction terms using Type II Wald Chi-square tests. Model assumptions were evaluated in all analysis frameworks. Indoor PM_{2.5} concentrations were natural-log transformed in the ITT-PM_{2.5} framework, and estimates are presented as percent difference in geometric mean PM_{2.5}.

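### Treatment-by-characteristic interactions on LRTI (yes/no) are tested only by Wald chi-square, which can miss strong effect modification if an arm-by-subgroup cell has few or no cases

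*Combined protocol and SAP*

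**What the plan says.** The effect-modification paragraph at the end of the Statistical Analysis Plan says that modification was examined "by a priori selected child, caregiver, and home characteristics within each of the model frameworks by including interaction terms in the primary model". It then gives one rule for all of them: "We assessed significance of the interaction terms using Type II Wald Chi-square tests". No likelihood-ratio, penalised or bootstrap alternative is named. There is no minimum cell count and no check for separation, only a general statement that model assumptions were evaluated. The modifiers are not listed.

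The ITT-LRTI model is a mixed effects logistic regression "with presence of LRTI (yes or no) as the outcome and assigned treatment as the exposure of interest". Treatment has three levels, so the interaction with a two-level characteristic has 2 degrees of freedom. The SAP's only remark on how often LRTI occurred explains the move away from count models: "very few children had more than one LRTI, resulting in under-dispersed data".

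On size, the project summary plans "a sample of 324 homes, or 108 within each study area", which "will be equally assigned to each of the three intervention arms". Item 6.1 of the IRB checklist adds, for western Montana: "We assume approximately 1.5 children under 5 years old per household".

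**The concern.** In a logistic model the Wald statistic is the squared estimate divided by its estimated variance. As an effect becomes extreme, the standard error can grow faster than the estimate, so the statistic shrinks (the Hauck-Donner effect). At the limit, a cell with no cases has an infinite maximum-likelihood log odds. The software stops at a large coefficient with an enormous standard error, and the statistic is effectively zero. The test is therefore weakest where an intervention works best in one subgroup, because that is the situation most likely to leave a cell nearly empty.

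At stake is the reading of the subgroup results for LRTI. A large difference in the effect of the filter or the education programme could carry an unremarkable p-value only because of the test chosen. The likelihood-ratio test compares the fit with and without the interaction and does not have this weakness.

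**Working it through.** **Inputs from the documents.** 324 homes, three equal arms, 1.5 children per home. Reproducing the plan's figure: 108 × 1.5 = 162 children in western Montana, as item 6.1 states. Applying 1.5 to all areas (an assumption) gives 324 × 1.5 = 486 children, or 486 / 3 = 162 per arm.

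**Assumptions not in the documents.** Two-sided 0.05. LRTI in 10%, 20% or 30% of rows. Subgroup of 20% (about 32 per arm) or 50% (81 per arm). True odds ratio 0.2 in one arm of the subgroup and 1 elsewhere. Independent rows, without random effects or the person-time covariate. One row per child (162 per arm), or two winters treated as independent rows (324 per arm).

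**Step 1: worked tables.** Take 32 children per arm in the subgroup and 130 outside it. For 2 df, p = exp(−statistic/2).

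- Subgroup cases 6/1/6, others 26/26/26. Interaction coefficient = ln[(1/31)/(6/26)] = −1.97; the other subgroup contributes ln 1 = 0. Variance = 1/1 + 1/31 + 1/6 + 1/26 + 2(1/26 + 1/104) = 1.33, SE 1.15. Wald p = 0.20; likelihood-ratio p = 0.092.
- Subgroup cases 6/0/6, others the same. The term 1/1 becomes 1/0. The fit stops at a coefficient of −16.3 with SE about 1300, and (16.3/1300)² ≈ 0.0002, so Wald p = 1.000. The likelihood-ratio statistic is 9.56, p = exp(−4.78) = 0.008.
- Subgroup cases 10/0/10, others 39/39/39. Wald p = 1.000; likelihood-ratio statistic 16.67, p = 0.0002.
- Subgroup cases 10/2/10, others 39/39/39. Wald p = 0.062; likelihood-ratio p = 0.023.

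**Step 2: how likely is an empty cell?** For one given cell the chance is (1 − p)^n.

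- No effect: 0.9^32 = 3.4%; 0.8^32 = 0.08%; 0.9^16 = 18.5%; 0.9^81 = 0.02%.
- Odds ratio 0.2: a 10% risk becomes 0.0222/1.0222 = 2.2%, and the chance of an empty cell of 32 is 49%. From 20% it is 21%, and from 30% it is 7%. For a cell of 81 at 30% it is 0.1%.

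**Step 3: power (1000 simulated data sets per row, odds ratio 0.2).**

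| Rows per arm | Subgroup | LRTI | Wald | Likelihood ratio |
|---|---|---|---|---|
| 162 | 20% | 10% | 0.9% | 25.7% |
| 162 | 20% | 20% | 11.2% | 44.7% |
| 162 | 20% | 30% | 37.2% | 60.1% |
| 162 | 50% | 10% | 17.0% | 41.6% |
| 162 | 50% | 20% | 55.3% | 64.5% |
| 162 | 50% | 30% | 80.0% | 82.8% |
| 324 | 20% | 10% | 9.7% | 45.3% |
| 324 | 20% | 20% | 59.3% | 75.3% |
| 324 | 20% | 30% | 87.7% | 90.9% |
| 324 | 50% | 20% | 91.1% | 92.0% |
| 324 | 50% | 30% | 98.2% | 98.4% |

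Repeat simulations agree to within a few points.

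**Step 4: false positives.** With no interaction, 162 rows per arm and a 20% subgroup, the rejection rates at 10/20/30% LRTI are 1.4/3.6/4.8% (Wald) and 7.5/6.3/5.6% (likelihood ratio). Wald is conservative in sparse cells and the likelihood ratio is mildly liberal, so part of its gain at 10% LRTI is inflated size.

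**Step 5: household random intercept.** With SD 1 (assumed), 162 children per arm, a 20% subgroup, 20% LRTI and 300 runs per case, power is 17% (Wald) against 30% (likelihood ratio) at a ratio of odds ratios of 0.3. At 0.1 it is 29% against 69%. The pattern survives clustering.

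**The case against.** **The outcome is not shown to be sparse.** A reader might infer from the SAP's remark on frequency that LRTI was rare. It says only that "very few children had more than one LRTI". The share with at least one is not given. The remark even points mildly the other way: for yes/no-like counts, variance over mean is about 1 − p, and under-dispersion marked enough to rule out count models is easier to see at 20% or 30% LRTI (ratio 0.8 or 0.7) than at 10% (0.9). This stands. Few-case cells are an assumption.

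**Cell sizes depend on unlisted modifiers.** Child sex, which item 6.1 expects to be balanced, would give about 81 per arm-by-sex cell, where the gap is small at 20% to 30% LRTI. The primary analysis probably uses both winters, since Winter 1 alone is a sensitivity analysis, and this could double the rows. Both points stand. With 324 rows and a 20% subgroup, however, the gap at 20% LRTI is still 59.3% against 75.3%.

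**Large gaps need large effects.** At a ratio of odds ratios of 0.5, with 162 rows, 20% LRTI and a 20% subgroup, power is 7% against 15%, so neither test is adequate. Size adjustment also narrows the gap: at 10% LRTI, a 20% subgroup and a ratio of 0.3, it goes from 1% against 20% to 6% against 13%. This stands, and a better test is only a partial remedy.

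**The other two frameworks.** A reader might extend the point to the exposure-response model, because the SAP names one test for every framework. There the exposure is continuous PM2.5, so there are no arm-by-subgroup cells, and none of the calculations covers it. The PM2.5 outcome model is linear and unaffected.

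**No conclusion of absence is written.** A reader might also infer that the plan declares modification absent when p is large. It states no such rule and no significance level. That reading would be wrong with either test.

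**Conclusion.** The point holds for the ITT-LRTI framework, in conditional form. The SAP's only test for these interactions loses power when an arm-by-subgroup cell has few cases and gives p near 1 when a cell has none, and no safeguard is stated. The loss is severe for small subgroups or low LRTI: at most about 37% power with Wald against 60% with the likelihood ratio in the 20%-subgroup, one-row-per-child cases, and 0.9% against 25.7% at the worst. It is about 1 point or less for balanced subgroups at 20% to 30% LRTI with two winters of rows. These figures rest on assumed LRTI proportions, subgroup shares and a strong interaction, in a simplified model. They show the size of the effect and do not reproduce the trial's model. Whether it occurred here cannot be judged without the case counts per cell. Effect modification is a secondary analysis, so this is a cheap improvement and not a threat to the main result.

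**What to change.** In the ITT-LRTI framework, test each interaction by a likelihood-ratio test between the glmer fits with and without the interaction, keeping the same random term. Where any arm-by-subgroup cell is empty or very small, take the p-value from a parametric bootstrap of that statistic. For every modifier, report LRTI cases and children per cell, with subgroup treatment estimates and intervals, and do not read non-significance as no modification. Wald tests can stay for the linear ITT-PM2.5 model. In the exposure-response model the likelihood-ratio test is optional.

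Cost: a short change to the SAP paragraph, an extra fit per modifier, and some bootstrap computing for the affected modifiers. As the SAP is written in the past tense, this means a re-analysis. Without the bootstrap, the likelihood-ratio test would be slightly liberal in the sparsest cells (about 6% to 8% at a nominal 5%).
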